## 11 Safety Analyses

Safety data, including AEs, clinical laboratory tests, vital signs, physical examinations, and concomitant medication usage will be summarized descriptively overall and by treatment group for the Safety Population. AEs include frequency of events and/or incidence of study subjects experiencing events, by study arm for the following:

- a) Study-defined treatment failures
- b) Study-defined treatment emergent AEs of special Interest
- c) All treatment-emergent AEs, total and by organ system classification
- d) All treatment-emergent AEs related to study medication, total and by organ system classification
- e) All treatment-emergent SAEs, total and by organ system classification
- f) All treatment-emergent SAEs related to study medication, total and by organ system classification
- g) All treatment-emergent AEs and SAEs that result in discontinuation of study medication
- h) Time to treatment failure
- i) Time to treatment-emergent AEs and SAEs resulting in premature discontinuation of study medication

For categorical safety outcomes, numbers and percentages will be used. For continuous safety outcomes, number, mean, standard deviation, median, interquartile range, minimum and maximum are used to summarize changes from baseline to each study visit in laboratory tests and vital signs. Percent change from baseline for laboratory values are summarized. The primary organ system associated with each adverse event was coded by the medical monitor. Kaplan-Meier methods are used to summarize graphically the time to treatment failure, and treatment-emergent AEs and SAEs that result in premature discontinuation of study medication.

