2.1.6 The Feasibility of Combining PFD with MMF for the Treatment of SSc-ILD

Directly relevant to this proposal, patients with SSc-ILD were randomized 1:1 in an initial safety and tolerability trial in patients with SSc-ILD (LOTUSS study, 20) to receive PFD when titrated from starting to final dose over a 2 week interval (one arm) vs a 4 week interval (second arm). Titration started at a dose of 801 mg/day and increased up to a maintenance dose of 2403 mg/day. Patients received PFD for 16 weeks in total and both treatment naïve patients and those already on other therapies, including treatment with MMF or CYC, were included in a stratified design. This design allowed an evaluation of whether the titration interval resulted in a difference in safety and tolerability and whether or not there were obvious differences when administered to treatment naïve patients or as an add-on therapy in combination with some form of immunosuppressive therapy. This trial Assessments included treatment-emergent AEs (TEAEs) and exploratory disease outcomes. Sixty-three patients were randomized; 96.8% experienced a TEAE and more patients reported TEAEs during the titration vs maintenance period consistent with the known pattern of TEAEs described when PFD has been used for the treatment of IPF. The most commonly reported TEAEs were also consistent with those observed for PFD when used in the treatment of IPF (nausea, headache, fatigue) and the frequency and type of TEAEs were similar regardless of titration schedule (Table 2.1.6a).

Table 2.1.6a. Summary of TEAEs in the LOTUSS Study.

TEAE ^a	Pirfenidone 2403 mg/day, number of patients (%)		
	2-week titration group (N = 32)	4-week titration group (N = 31)	Total (N = 63)
At least one TEAE	31 (96.9)	30 (96.8)	61 (96.8)
Maximal intensity of TEAE ^b			
Mild	7 (21.9)	12 (38.7)	19 (30.2)
Moderate	15 (46.9)	15 (48.4)	30 (47.6)
Severe	9 (28.1)	3 (9.7)	12 (19.0)
Life-threatening	0	0	0
Relationship of TEAE to study treatment ^{c,d}			
Not related	3 (9.4)	2 (6.5)	5 (7.9)
Possibly related	7 (21.9)	6 (19.4)	13 (20.6)
Related	21 (65.6)	22 (71.0)	43 (68.3)
At least one TE SAE	3 (9.4)	0	3 (4.8)
At least one treatment-related TE SAE	1 (3.1)	0	1 (1.6)
Discontinuation of study treatment due to TEAE	5 (15.6)	1 (3.2)	6 (9.5)
Death as an outcome of a TEAE	0	0	0

	Pirfenidone 2403 mg/day, number of patients (%)		
	2-week titration group (N = 32)	4-week titration group (N = 31)	Total (N = 63)
	TEAEs reported in ≥10% of patients overall		

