- c) ***Gastrointestinal Disorders.*** In the clinical studies, gastrointestinal events of nausea, diarrhea, dyspepsia, vomiting, gastro-esophageal reflux disease, and abdominal pain were more frequently reported by patients in the PFD treatment groups than in those taking placebo. Dosage reduction or interruption for gastrointestinal events was required in 18.5% of patients in the 2403 mg/day group, as compared to 5.8% of patients in the placebo group; 2.2% of patients in the PFD 2403 mg/day group

discontinued treatment due to a gastrointestinal event, as compared to 1.0% in the placebo group. The most common (>2%) gastrointestinal events that led to dosage reduction or interruption were nausea, diarrhea, vomiting, and dyspepsia. The incidence of gastrointestinal events was highest early in the course of treatment (with highest incidence occurring during the initial 3 months) and decreased over time. Dosage modifications may be necessary in some cases of gastrointestinal adverse reactions.

2.3.1.2.4 Adverse Events reported during the treatment of IPF:

Adverse reactions related to Liver Enzyme Elevations, Photosensitivity Reaction or Rash, and Gastrointestinal Disorders represent the principal adverse reactions associated with the administration of PFD and have already been described in the Warnings section above and are detailed in the Investigational Brochure (11).

The safety of PFD has been evaluated in more than 1400 subjects with over 170 subjects exposed to PFD for more than 5 years in clinical trials. PFD was studied in 3 randomized, double-blind, placebo-controlled trials (Studies 1, 2, and 3) in which a total of 623 patients received 2403 mg/day of PFD and 624 patients received placebo. Subjects ages ranged from 40 to 80 years (mean age of 67 years). Most patients were male (74%) and Caucasian (95%). The mean duration of exposure to PFD was 62 weeks (range: 2 to 118 weeks) in these 3 trials.

At the recommended dosage of 2403 mg/day, 14.6% of patients on PFD compared to 9.6% on placebo permanently discontinued treatment because of an adverse event. The most common (>1%) adverse reactions leading to discontinuation were rash and nausea. The most common (>3%) adverse reactions leading to dosage reduction or interruption were rash, nausea, diarrhea, and photosensitivity reaction.

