8.3 ADVERSE EVENT REPORTING

A consistent methodology for eliciting AEs will be used at all subject evaluation time points that includes open-ended questions such as:

- "How have you felt since your last clinical visit?"
- "Have you had any new or changed health problems since you were last here?"

The occurrence of an AE or SAE may come to the attention of study personnel during study visits and interviews of a study participant presenting for medical care, or upon review by a study monitor. All AEs including local and systemic reactions not meeting the criteria for SAEs will be captured on the appropriate CRF. Information to be collected includes event description, time of onset, clinician's assessment of severity, relationship to study product (assessed only by those with the training and authority to make a diagnosis), and time of resolution/stabilization of the event. All AEs occurring while

on study must be documented appropriately regardless of relationship. All AEs will be followed to adequate resolution.

Any medical condition that is present at the time that the participant is screened will be considered as baseline and not reported as an AE. However, if the study participant's condition deteriorates at any time during the study (in frequency, severity or character), it will be recorded as an AE and a descriptor will be used as a modifier term to convey that it relates to a pre-existing condition that has changed (e.g. "more frequent headaches"). UPs will be recorded in the data collection system throughout the study.

Changes in the severity of an AE will be documented to allow an assessment of the duration of the event at each level of severity to be performed. AEs characterized as intermittent require documentation of onset and duration of each episode.

The Principal Investigator is responsible for ensuring that all AEs and SAEs that are observed or reported during the study, are collected and reported to the FDA, appropriate IRB(s), and to Genentech, Inc. in accordance with CFR 312.32 (IND Safety Reports).

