### 11.2.2 AEs of Special Interest

AEs of Special Interest represent a specific subset of all AEs and are defined by the study protocol based on two distinct features: 1) their likely association with the investigational drug(s), and 2) the presence of pre-specified study drug management guidelines that are to be followed when the AE occurs.

AEs meeting the following criteria will be classified and reported as AEs of Special Interest in addition to their inclusion in the overall frequency and incidence of AEs.

- Leukopenia, defined as  $WBC \leq 2.5 \times 10^3/\mu\text{l}$  of blood
- Neutropenia, defined as an absolute neutrophil count  $< 1.0 \times 10^3/\mu\text{l}$  of blood
- Clinically significant anemia, defined as blood hemoglobin  $< 10.0 \text{ gm/dl}$  or a drop in hemoglobin to  $< 9.0 \text{ gm/dl}$  if the baseline hemoglobin was  $< 11.0 \text{ gm/dl}$
- Liver enzyme elevations that exceed  $3 \times$  the upper limit of normal (ULN) ALT and/or AST.
- New onset or worsening of existing gastrointestinal symptoms that do not respond to medical management and are of sufficient clinical importance to warrant drug dose adjustment (including nausea, diarrhea, vomiting, and dyspepsia).
- Documentation of gastrointestinal ulcer, gastrointestinal bleeding or abdominal emergency
- Infection requiring hospitalization, intravenous antibiotics, or judged as requiring the withdrawal of immune suppression for effective treatment.
- New or reactivated viral infections including PVAN, JC virus associated PML, CMV infections, reactivation of HBV or HCV.
- Photosensitivity skin reactions that do not respond to sunscreen, avoidance, and as-needed use of over the counter topical creams, and are of sufficient clinical importance to warrant drug dose adjustment.
- Development of a proven malignancy other than basal cell cancer of the skin or cervical carcinoma in situ removed entirely by biopsy.
- Angioedema

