## 11.5 Classification of an Adverse Event

### 11.5.1 Severity of Event

The intensity of all AEs will be graded using a five-point grading scale in which the following descriptions of severity will apply. Note that for some AEs, Grades 4 and/or 5 may not be applicable. In those cases only 3 different grades (Grade 1-3) are to be considered:

8.2.1.1	Grade 1:	"Mild"; asymptomatic or mild symptoms; clinical or diagnostic observations only; intervention not indicated.
8.2.1.2	Grade 2:	"Moderate"; minimal, local or noninvasive intervention indicated; limiting age-appropriate instrumental ADL*.
8.2.1.3	Grade 3:	"Severe"; medically significant but not immediately life-threatening; hospitalization or prolongation of hospitalization indicated; disabling; limiting self care ADL**.
8.2.1.4	Grade 4:	"Life-threatening consequences"; urgent intervention indicated.
8.2.1.5	Grade 5:	"Death related to AE".

---

\*Instrumental ADL refer to preparing meals, shopping for groceries or clothes, using the telephone, managing money, etc.

\*\*Self care ADL refer to bathing, dressing and undressing, feeding self, using the toilet, taking medications, and not bedridden.

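### SAP 11 specifies no adverse-event output by severity grade, although every AE is graded 1 to 5 and the secondary objective is the absence of limiting toxicity; dose adjustment is captured only for gastrointestinal and photosensitivity events

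*SAP*

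**What the plan says.** **Objective.** Protocol 3 and SAP 5.1.2 set as the secondary objective that pirfenidone plus MMF is well tolerated relative to MMF alone, without limiting toxicity that affects the overall treatment effect.

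**What is recorded.** SAP 11.5.1 and Protocol 8.2.1 grade all events: "The intensity of all AEs will be graded using a five-point grading scale". Protocol 8.3 goes further: "Changes in the severity of an AE will be documented to allow an assessment of the duration of the event", that is, its duration at each level of severity.

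**What is reported.** SAP 11 lists items a to i:
- treatment failures;
- AESIs ("Study-defined treatment emergent AEs of special Interest");
- TEAEs ("All treatment-emergent AEs, total and by organ system classification");
- related TEAEs;
- SAEs and related SAEs;
- AEs and SAEs that end study medication;
- two time-to-event items.

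No item is split by grade. Secondary endpoint 10 in SAP 5.2.2 is time to stopping drug for any reason, plus related TEAEs by organ class. Protocol 8.1 and 10.4.4 (safety) and 10.4.10 (individual tabulations) do not use the grade.

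**Dose modification.** Among the AESIs in SAP 11.2.2, the gastrointestinal item covers symptoms that do not respond to medical management and "are of sufficient clinical importance to warrant drug dose adjustment (including nausea, diarrhea, vomiting, and dyspepsia". The photosensitivity item has the same dose-adjustment condition. SAP 9.4 and 6.4.3.5 report, by arm, the proportions reaching and sustaining the maximum dose, time at that dose, and adherence both per protocol and as prescribed by the site. None of these is tied to an AE.

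**The concern.** An event count treats a mild and a severe nausea alike. The plan collects the grade and then names no output that uses it, so an excess of severe events in one arm need not appear in any specified table. The nearest substitutes measure other things. SAEs depend on outcome criteria such as hospitalization, stops depend on the decision to end treatment, and relatedness is a causality judgement.

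There is also a narrower gap for dose-limiting events. Of the reactions in the IPF trials, Protocol 2.3.1.2.4 says: "The most common (>3%) adverse reactions leading to dosage reduction or interruption were rash, nausea, diarrhea, and photosensitivity reaction". Rash is named first there, yet it is not an AESI. AESIs are defined partly by having a pre-specified drug-management guideline, and Protocol 6.1.5.2 f gives one for photosensitivity or rash. Rash that leads to a dose change is therefore counted as a TEAE but not identified as dose-limiting. At stake is whether the report can answer the secondary objective directly.

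**Working it through.** **1. Reproduce the protocol's figures for LOTUSS (Protocol 2.1.6, Table 2.1.6a).** The protocol states: "Sixty-three patients were randomized; 96.8% experienced a TEAE".
- Any TEAE: 31/32 = 96.9%, 30/31 = 96.8%, total 61/63 = 96.8%. This agrees.
- Maximum intensity: 19 mild + 30 moderate + 12 severe = 61. This agrees with the number having any TEAE.

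**2. Set severity beside the analogues of the planned outputs, 2-week against 4-week titration.**

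| Measure in LOTUSS | 2-week (N = 32) | 4-week (N = 31) | Difference (points) | Planned in SAP? |
|---|---|---|---|---|
| Any TEAE | 31 (96.9%) | 30 (96.8%) | 0.1 | yes, item c |
| GI organ class | 24 (75.0%) | 25 (80.6%) | -5.6 | yes, item c |
| Related TEAE | 21 (65.6%) | 22 (71.0%) | -5.4 | yes, item d and endpoint 10b |
| Treatment-emergent SAE | 3 (9.4%) | 0 | 9.4 | yes, item e |
| Stop due to TEAE | 5 (15.6%) | 1 (3.2%) | 12.4 | yes, item g |
| Severe TEAE | 9 (28.1%) | 3 (9.7%) | 18.4 | none specified |

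The related row counts only the category headed related in that table, without the possibly related category.

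**3. Precision of the severe-TEAE contrast.** The standard error is √(0.281 × 0.719/32 + 0.097 × 0.903/31) = 0.0956. The 95% CI is 18.4 ± 1.96 × 9.56, or about -0.3 to 37.2 points; Fisher's exact p = 0.11. The contrast illustrates the measure and does not establish a difference.

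**4. Can SAEs stand in for severity?** Severe TEAEs occurred in 12/63 = 19.0% and treatment-emergent SAEs in 3/63 = 4.8%. Even if all three participants with an SAE were among the severe cases, 12 − 3 = 9 had a severe TEAE without an SAE.

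**5. Can stops stand in?** Only in part. Protocol 2.3.1.2.5 names diarrhea and nausea among the most common severe events in LOTUSS, and says that no gastrointestinal event led to discontinuation.

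**6. What the dose-adjustment outputs cover (Protocol 2.3.1.2, IPF trials).** "Dosage reduction or interruption for gastrointestinal events was required in 18.5% of patients in the 2403 mg/day group, as compared to 5.8" per cent on placebo, a gap of 18.5 − 5.8 = 12.7 points. The GI AESI largely captures these events. It does not capture rash, which occurred in 30% against 10% on placebo in the IPF trials (Table 2.3.1.2.4a) and in 20.6% in LOTUSS, where photosensitivity was 6.3%.

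**7. What a grade table could show here.** SAP 10.1 indexes 51 participants in the efficacy model. Assume a 25/26 split, which the documents do not give, and severe rates of 19% (LOTUSS overall) against 9.5% (half of that, for illustration). The expected counts are 25 × 0.19 = 4.8 and 26 × 0.095 = 2.5. The difference is 9.5 ± 1.96 × √(0.19 × 0.81/25 + 0.095 × 0.905/26) = 9.5 ± 19.1, or about -9.6 to 28.6 points. The table would be descriptive only.

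**The case against.** The strongest reply is that the plan already has a broad set of safety outputs, and much of it stands.

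- A reader might infer that no output uses AE-driven dose changes. The documents do not support that: item b counts GI and photosensitivity AESIs, both defined by a dose adjustment. The GI item names nausea, diarrhea, vomiting and dyspepsia, the same four that Protocol 2.3.1.2.3 gives as the most common GI causes of dose change.
- A reader might also infer that the tolerability comparison rests on an any-TEAE rate near 97% plus rare stops. It does not. The any-TEAE total is one line of item c. The tolerability endpoint is time to stopping and related TEAEs by organ class, and SAEs and AESIs are reported as well. Stops for any AE are not rare: 6/63 = 9.5% in LOTUSS and 14.6% against 9.6% in the IPF trials. Only GI stops were rare there, at 2.2% against 1.0%.
- Planned measures can separate groups. In LOTUSS both SAEs and stops did, and LOTUSS compared two titration speeds, not pirfenidone with placebo.
- In a blinded randomized trial, a between-arm difference in dose attained (SAP 9.4) is informative without attributing each change to an event.
- The table shells are in a separate document (SAP 16) that was not available, so a grade table may exist there.

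What remains is that none of these measures is severity, and that rash leading to a dose change is not identified. The outputs that bear on a stated objective should be named in the SAP even if the shells contain them.

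**Conclusion.** The point holds in a limited form. SAP 11 and Protocol 8.1, 10.4.4 and 10.4.10 specify no AE output by severity grade, although the grade is collected for every event. Dose adjustment is captured only for GI and photosensitivity AESIs, and the dose summaries are not linked to AEs. In LOTUSS severity carried information that the SAE count did not: at least 9 of the 12 participants with a severe TEAE had no SAE. The 18.4-point gap between titration groups is imprecise and does not forecast the effect in this trial.

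This is an omission in reporting, not a flaw that invalidates the safety analysis. The conclusion rests on the lists in the SAP and protocol being complete and on severity having been recorded as planned. The 25/26 split is an assumption, and 51 is the number in the efficacy model; the Safety Population may differ.

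**What to change.** 1. Add to SAP 11, for the Safety Population by arm and labelled descriptive: participants by maximum TEAE grade, and participants with any grade 3 or higher TEAE, in total and by organ class, with the between-arm difference and 95% CI.
2. Where the medication log (Form 027) can be linked to the AE records (Forms 044 and 045), add a listing of TEAEs, including rash, that led to dose reduction or temporary hold, separately for MMF and for PFD/Plac. If the link cannot be made reliably, say so in the SAP and rely on item b and SAP 9.4.

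**Cost.** The first item needs SAP wording and one table, with no new data, because Protocol 8.3 lists severity among the information collected for each AE. The second may need derivation work: the AE content listed there has no field for action taken on study drug, so feasibility has to be checked before it is promised. The downside is more tables with small counts and wide intervals, which should be presented without formal inference.

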### 11.1 Extent of Exposure

Total participant months of exposure to study medication is defined as the number of days from date of last dose of study medication minus the date of the first dose of study medication plus one. It is converted to months by divided the total number of days by 28. It is summarized descriptively by treatment group. Both full and partial amount of drug received is counted in the assessment of exposure.

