5.3.3 Handling of Premature Participant Withdrawals

Should a participant prematurely discontinue all active drug treatment for any reason, he/she will be asked to return for key outcome determinations at 12 and 18 months. Their clinical management during the intervals between these visits will be at the discretion of the patient and their treating physician. At the 12 and 18 month visits, any medication prescribed by their treating physician since discontinuing study drug treatment will be recorded in addition to other required assessments for the 12 and 18-month visits. The participant will also be asked to participate in an exit visit, either by phone or in person, to document the reason for withdrawal and the status of the participant at the time of the withdrawal. Should the participant die, the cause of death will be determined and recorded if possible. This additional data will be utilized in the statistical analysis of the primary and secondary study outcomes as defined by the statistical plan.

If only PFD/Plac is prematurely discontinued, and the participant continues to take MMF according to the protocol, then they will continue their participation in all study visits according to the normal study protocol.

If MMF is prematurely discontinued, the participant must stop the PFD/Plac study medication as well and will be asked to return for key outcome determinations at 12 and 18 months. Their clinical management during the intervals between these visits will be at the discretion of the patient and their treating physician. At the 12 and 18 month visits, any medication prescribed by their treating physician since discontinuing study drug treatment will be recorded in addition to other required assessments for the 12 and 18-month visits.

Participants who completely withdraw from the study (drop out; end their participation entirely) will be asked to participate in an exit visit, either by phone or in person, to document the reason for withdrawal and the status of the participant at the time of the withdrawal. Should the participant die, the cause of death will be determined and recorded if possible.

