6.1.5 Pre-specified Dose Adjustment & Modifications

The toxicity profiles for MMF and PFD are well established as outlined in Section 2.3 and drug discontinuation and/or dose modification should be managed in a manner consistent with the following criteria in order to provide a nearly uniform response to pre-defined toxicity at all centers. However, in clinical situations that fall outside of these parameters and if warranted based on good clinical practice, a site investigator may independently modify drug dosing as needed to assure patient safety. If such a change is required, the reasons for the deviation are to be documented and the Executive Committee notified within 3 days. Medications that are contraindicated while on treatment with the study drugs are detailed separately in Section 7.5.

In the event that one study drug is permanently discontinued due to tolerability, adverse event or other medical consideration, then continued use of the remaining study drug will be according to the following pre-specified management:

- If only PFD/Plac is permanently discontinued, the participant may continue to take MMF according to the protocol and continue their participation in all study visits according to the normal protocol-defined schedule of events.
- If MMF is prematurely discontinued, the participant must stop the PFD/Plac study medication as well and will be asked to return for key outcome determinations at 12 and 18 months as detailed in Section 5.3.3 (Handling of Premature Participant Withdrawals).

6.1.5.1 Pre-specified dose adjustments for MMF.

The following abnormalities and laboratory test monitoring results require study drug adjustment, either temporary (until normalization) or permanent, as indicated by the nature of the event, its severity and/or course of resolution upon discontinuation of therapy.

- a) Allergic reaction associated with the administration of MMF.

Dose Management: Study drug will be stopped and subject withdrawn from study.

b) Evidence of clinically significant Bone Marrow Suppression including any one or more of the following

- WBC $<2.5 \times 10^3/\mu\text{l}$
- Absolute neutrophil count $<1.0 \times 10^3/\mu\text{l}$
- Platelet count $<100.0 \times 10^3/\mu\text{l}$
- Hemoglobin $< 10.0 \text{ gm/dl}$ or a drop in hemoglobin to $< 9.0 \text{ gm/dl}$ if the baseline hemoglobin was $< 11.0 \text{ gm/dl}$

Dose Management: Management as follows:

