#### 8.2.2 Per Protocol Population

The Per Protocol (PP) analysis set consists of all participants in the m-ITT population who completed 18 months of study medication (i.e., both MMF and PFD/Plac) and do not have a major protocol violation, defined as violation of entry criteria or taking prohibited medications. The study window for month 18 visit is  $\pm$  6 weeks. Membership in the PP analysis population was determined before study unblinding.

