### 9.4 Treatment Compliance

Compliance with study medication (MMF and PFD/Plac) is assessed and summarized, including

- the proportion of participants who adhered to study treatment, overall and at each study visit,
- the median duration of adherence to study treatment (defined in section 11.1),
- the proportion of participants reaching maximum dose,
- the proportion of participants who sustain their maximum dose,
- the time to reach the maximum dose, and
- the time remaining at the maximum dose.

These are calculated and summarized overall and by treatment group. The maximum dose is 12 pills/day for MMF (1500 mg) and 9 pills/day for PFD (801 mg)/Plac. The proportion of the maximum dose that the participants reached during study period is summarized overall and by treatment group. Participants were expected to take study medication unless it was permanently discontinued due to an AE. The study medication log (Form 027), adverse event form (Form 044), serious adverse event form (Form 045) and final status form (Form 035) are used to derive the compliance measure.

The proportion of participants who permanently discontinued study medication will be summarized with descriptive statistics, overall and by treatment group. A Kaplan-Meier curve will present the time to permanent discontinuation of study medication by treatment group. A listing of these participants with their reason for permanent discontinuation of study medication will be provided.

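### SAP 11.1 counts exposure as one first-to-last-dose span without separating MMF from PFD/Plac or subtracting holds, and SAP 9.4 reuses it as duration of adherence, so descriptive summaries can overstate PFD/Plac exposure

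*SAP*

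**What the plan says.** SAP 11.1 gives a single formula per participant: "the number of days from date of last dose of study medication minus the date of the first dose of study medication plus one". Days are then turned into months of 28 days each. On reporting, the section says only this: "It is summarized descriptively by treatment group". Full and partial amounts both count, which deals with dose level but not with gaps in dosing. The section does not say which drug supplies the two dates, or what to do when the drugs stop on different days.

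Elsewhere the SAP uses the same term for the two drugs. Section 9.4 opens with "Compliance with study medication (MMF and PFD/Plac) is assessed and summarized", and the per-protocol set in 8.2.2 requires participants to have "completed 18 months of study medication (i.e., both MMF and PFD/Plac"). Among its compliance summaries, 9.4 lists "the median duration of adherence to study treatment (defined in section 11.1").

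Protocol 6.1.5 provides: "If only PFD/Plac is permanently discontinued, the participant may continue to take MMF according to the protocol". Section 5.3.3 ("If only PFD/Plac is prematurely discontinued, and the participant continues to take MMF according to the protocol") keeps such participants on the normal visit schedule, and 7.2.5 repeats the arrangement. All three sections also require PFD/Plac to stop when MMF is stopped prematurely.

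**The concern.** MMF is background treatment in both arms, and PFD/Plac is the randomized component. Under the permanent-discontinuation rules, MMF can outlast PFD/Plac but not the reverse, so the last dose of study medication will normally be an MMF dose. A single span then measures time on the background drug and says little about how long the randomized drug was taken.

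Calling the same span duration of adherence adds a second problem. A participant who is off a drug during a hold, or off PFD/Plac permanently, is still counted as adherent for the whole interval.

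What is at stake is the description of exposure and adherence. Readers use it to judge how much pirfenidone the combination arm received, and it gives context to the secondary objective on tolerability.

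**Working it through.** **Inputs.** Exposure formula and 28-day month: SAP 11.1. Month 18 = 504 days: schedule in SAP 6.4. Intended duration 18 months for all study drugs: Protocol 6.1.6. MMF may be off for up to 60 days with the participant remaining in the study: Protocol 17.2.2(g). Permanent discontinuation for adverse events in the IPF trials, 14.6% on PFD and 9.6% on placebo: Protocol 2.3.1.2.4. The model in SAP 10.1 indexes 51 participants, so about 25 per arm is assumed.

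**Reproducing the plan's 18 months.** With first dose on day 0 and last dose on day 503, (503 − 0 + 1)/28 = 504/28 = 18.0. A last dose on day 504 gives 505/28 = 18.04.

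**One participant.** Both drugs start on day 0, PFD/Plac stops early, and MMF runs to day 503.

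| PFD/Plac taken for | PFD/Plac alone (months) | SAP 11.1 read literally (months) | Excess (months) |
|---|---|---|---|
| 1 month | 28/28 = 1.0 | 18.0 | 17.0 |
| 8 weeks | 56/28 = 2.0 | 18.0 | 16.0 |
| 3 months | 84/28 = 3.0 | 18.0 | 15.0 |
| 6 months | 168/28 = 6.0 | 18.0 | 12.0 |
| 12 months | 336/28 = 12.0 | 18.0 | 6.0 |

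**Holds.** A 60-day interruption inside the span is not subtracted: 60/28 = 2.1 months, and 2.1/18 is about 12% of the treatment period.

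**One arm of 25.** Assume k participants stop PFD/Plac at month 3, everyone continues MMF to month 18, and no one else stops. Mean PFD/Plac exposure is (3k + 18(25 − k))/25.

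| k of 25 | Mean, PFD/Plac (months) | Median, PFD/Plac (months) | SAP 11.1 mean and median (months) |
|---|---|---|---|
| 2 | 16.8 | 18.0 | 18.0 |
| 4 (whole number nearest 14.6%) | 15.6 | 18.0 | 18.0 |
| 8 | 13.2 | 18.0 | 18.0 |
| 10 | 12.0 | 18.0 | 18.0 |
| 15 | 9.0 | 3.0 | 18.0 |

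The median of 25 is the 13th ordered value, so it moves only when 13 or more stop.

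**Difference between arms at the IPF rates.** If every stopper stops at week 8 and continues MMF, each loses 18 − 2 = 16 months of PFD/Plac. The mean overstatement is 0.146 × 16 = 2.3 months on PFD and 0.096 × 16 = 1.5 months on placebo. The hidden difference is 0.050 × 16 = 0.8 months. A 5.0-point gap is 0.05 × 25 = 1.25 participants per arm.

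**The case against.** The strongest reply is that 11.1 is a descriptive summary with no test attached, and that the plan measures tolerability elsewhere. This is correct. A reader might infer that the rule makes the arms look alike on the measure meant to reveal a tolerability difference. The documents do not support that. SAP 5.2.2 item 10 defines tolerability as time to withdrawal or removal from active drug therapy, plus treatment-related adverse events by organ class. SAP 11 adds events leading to discontinuation. None of these uses the 11.1 formula.

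Other parts of the reply also stand:

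- Pooling of the two drugs is inferred from usage in 9.4 and 8.2.2. Section 11.1 does not state it, and the table shells are a separate document (SAP 16), so a per-drug table cannot be excluded.
- Not every participant who stops PFD/Plac stays on MMF. Protocol 6.1.5 says the participant may continue MMF, while 6.1.5.2(c), (d) and (i) describe withdrawal from the study or from its treatment phase. The documents do not settle how many would remain on MMF, and these clauses should be reconciled.
- It would be too strong to say that the overstatement falls mostly in the PFD arm. At the IPF rates, 9.6/(14.6 + 9.6), about 40% of stoppers, would be on placebo, and those rates come from another disease.
- The two pill-count ratios in SAP 6.4.3.5 use pills prescribed by protocol and pills prescribed by the site, so comparing them partly captures holds.
- SAP 9.4 already plans a Kaplan-Meier curve and a listing of permanent discontinuations, and its maximum-dose measures are set for each drug.

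These measures do not fill the gap. The maximum-dose measures do not give time on PFD/Plac at any dose. The pill-count ratios cover only the time on study medication, and both they and the Kaplan-Meier curve leave the drug unspecified. The listing shows cases but does not summarize duration.

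**Conclusion.** The point holds for the descriptive summaries of exposure and duration of adherence. As written, the rule credits a participant who stops PFD/Plac and continues MMF with exposure up to the last MMF dose. In the 8-week example that is 18.0 months against 2.0. If MMF ends before month 18, the credit ends there too. The mean and distribution are affected. In the arm-level illustration the mean falls from 18.0 to 15.6 months when 4 of 25 stop at month 3, and to 13.2 when 8 of 25 stop. The median, which is what 9.4 reports, stays at 18.0 until about half stop.

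This rests on three assumptions: that study medication in 11.1 has the two-drug meaning it has in 9.4 and 8.2.2, that the participants concerned do continue MMF, and that the unseen table shells do not split by drug. The stopping rates and times are illustrative; nothing in the documents gives them for this trial.

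**What to change.** In SAP 11.1, compute and summarize exposure separately for MMF and for PFD/Plac, by treatment group. Give it in two forms: first-to-last-dose time, and days on drug net of recorded holds. Derive both from the study medication log (Form 027), which 9.4 already names as a source.

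In SAP 9.4, replace the cross-reference to 11.1 with days on each drug net of holds as the duration of adherence. Time to permanent discontinuation should not take that role, because it too ignores temporary holds. Present the Kaplan-Meier of permanent discontinuation separately for each drug. If the table shells already split exposure by drug, the SAP text should say so.

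The cost is SAP wording and programming.
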